Known	Known	
If start date < first IP taken date, then:
 
If stop date < first IP taken date, assign as prior
 
Else if stop date >= first IP taken date, assign as Concomitant.
 
If start date >= first IP taken date, assign as concomitant

	Partial	
Impute stop date as latest possible date (i.e. last day of month if day unknown or 31st December if day and month are unknown), then:
 
If start date < first IP taken date, then:
 
If stop date < first IP taken date, assign as prior
 
Else if stop date >= first IP taken date, assign as Concomitant.
 
If start date >= first IP taken date, assign as concomitant

	Missing	Assign as concomitant

Document:

Author:

Version Number:

Version Date:

Final v1.0

10Sep2019

Template No: CS\_TP\_BS016 Revision 4

Effective Date: 01Apr2016

Reference: CS\_WI\_BS005

START DATE	STOP DATE	ACTION
Partial	Known	
Impute start date as earliest possible date (i.e. first day of month if day unknown or 1st January if day and month are unknown), then:
 
If start date < first IP taken date, then:
 
If stop date < first IP taken date, assign as prior
 
Else if stop date >= first IP taken date, assign as Concomitant.
 
If start date >= first IP taken date, assign as concomitant

	Partial	
Impute start date as earliest possible date (i.e. first day of month if day unknown or 1st January if day and month are unknown) and impute stop date as latest possible date (i.e. last day of month if day unknown or 31st December if day and month are unknown), then:
 
If start date < first IP taken date, then:
 
If stop date < first IP taken date, assign as prior
 
Else if stop date >= first IP taken date, assign as Concomitant.
 
If start date >= first IP taken date, assign as concomitant

	Missing	Assign as concomitant

Document:  
 Author:

Version Number:  
 Version Date:

Final v1.0  
 10Sep2019

Template No: CS\_TP\_BS016 Revision 4  
 Effective Date: 01Apr2016

Reference: CS\_WI\_BS005

START DATE	STOP DATE	ACTION
Missing	Known	No imputation for missing start date  If stop date < first IP taken date, assign as prior  Others assign as concomitant
	Partial	No imputation for missing start date; impute stop date as latest possible date (i.e. last day of month if day unknown or 31st December if day and month are unknown), then:  If stop date < first IP taken date assign as prior  Others assign as concomitant
	Missing	Assign as concomitant

Document:  
 Author:

Version Number:  
 Version Date:

Final v1.0  
 10Sep2019

Template No: CS\_TP\_BS016 Revision 4  
 Effective Date: 01Apr2016

Reference: CS\_WI\_BS005

## APPENDIX 2. DATA EXTRACTION RULE

- a. **AE** domain: take all AEs if AE start date (imputed date will be used if partial date available)  $\leq$  cut-off date

If AE start date  $\leq$  cut-off date  $<$  AE end date (i.e., resolved after cut-off date), then the AE will be considered as “Ongoing” for reporting. AE outcome will programming changed as “NOT RECOVERED/NOT RESOLVED”

- b. **CM** domain: take all CMs if CM start date (imputed date will be used if partial date available)  $\leq$  cut-off date

If CM start date  $\leq$  cut-off date  $<$  CM end date (i.e., medication ended after cut-off date), then the CM will be considered as “Ongoing” for reporting.

- h. **Other** domains:

Use --DTC or --STDTC depending on domain

Take all data if --DTC or --STDTC  $\leq$  cut-off date

---

Document:

Author:

Version Number:

Final v1.0

Version Date:

10Sep2019

Template No: CS\_TP\_BS016 Revision 4

Reference: CS\_WI\_BS005

Effective Date: 01Apr2016

### APPENDIX 3. PROTOCOL DEVIATION SPECIFICATION

Deviation code	DVOECOD (Category)	*****Simple*****	Additional Description for PD detection	Study Part	Timepoint	DMCAT	program/Source data verification?	Excluded from the PP	Excluded from the PP2	Excluded from the PK	Excluded from the PD
		DVTERM (PD Description)									
I01	Eligibility and Entry Criteria	Male or female age out of range (< 18 or >80 years) at Screening		A, B	Screening	Major	program	Yes	Yes		
E01	Eligibility and Entry Criteria	Previous usage of any biological agents including any TNF-alpha inhibitor prior to Randomisation	Refer ATC CODE for prohibited medication to get this PD.		Week 0 (Randomisation)	Major	program	Yes	Yes		
D01	Withdrawal Criteria	Subject still receive IPs even though serious infection including active TB or opportunistic infection	from adverse event data; if not, source data verification		All visits from Randomisation	Major	program and manual review	No	No		
C01	Study Procedures Criteria	More than 6 weeks from Screening to randomisation (+1 week window allowed if the subject is still eligible at the Randomisation for ESR/CRP and major safety lab)	More than 6 weeks from Screening to randomisation (+1 week window allowed if the subject is still eligible at the Randomisation for ESR/CRP and major safety lab)		Week 0 (Randomisation)	Major	program and manual review	Yes	Yes		
C02	Study Procedures Criteria	Week 24/Visit 5 window deviation (out of +/- 5 days)	Week 24/Visit 5 window deviation (out of +/- 5 days)		Week 24/Visit 5	Major	program and manual review	No	No		
C1E	Study Procedures Criteria	ACR component (CRP) assessed after IP injection at Randomisation	ACR component (CRP) assessed after IP injection at Week 0 (Randomisation) regardless IP time is unknown or missing		Week 0	Major	Source data verification	Yes	Yes		
C2E	Study Procedures Criteria	Chest x-ray assessed earlier than 3 months prior to Screening or after Randomisation, if >100 days prior to Screening or after Randomisation, exclude from PPS1 and PPS2	Chest x-ray assessed earlier than 3 months prior to Screening or after Randomisation, if >100 days prior to Screening or after Randomisation, exclude from PPS1 and PPS2		Week 0	Major	program and source data verification	Yes, if >100 days prior to Screening or after Randomisation	Yes, if >100 days prior to Screening or after Randomisation		

Document:  
 Author:

Version Number:  
 Version Date:

Final v1.0  
 10Sep2019

Template No: CS\_TP\_BS016 Revision 4  
 Effective Date: 01Apr2016

Reference: CS\_WI\_BS005

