ADR adverse drug reaction; AE adverse event; AESI adverse event of special interest; ALT alanine aminotransferase; AST aspartate aminotransferase; BUN blood urea nitrogen; BSA body surface area; CR complete response; CT computerized tomography; DNA deoxyribonucleic acid; ECG electrocardiogram; ECOG Eastern Cooperative Oncology Group; EOS End of study; FACS fluorescence-activated cell sorting; FL follicular lymphoma; HACA human antichimeric antibody; HBcAb hepatitis B core antibody; HBsAg hepatitis B surface antigen; HBV hepatitis B virus; HCV hepatitis C virus; HIV human immunodeficiency virus; i.v. intravenous; IWG International Working Group; IXRS Interactive Voice Telephone and Web Response System; LDH lactate dehydrogenase; PCR polymerase chain reaction; PD pharmacodynamics; PE physical examination; PET positron emission tomography; PML progressive multifocal leukoencephalopathy; PK pharmacokinetic; SAE serious adverse event; TB tuberculosis; WHO World Health Organization.

- a Most screening assessments should be conducted within 30 days of Day 1. However, the screening CT scan and bone marrow biopsy may be conducted within 60 days before randomization. The total screening period is not to exceed 60 days in this case.
- b Patients who withdraw consent from the study will have no further investigations performed after their withdrawal.
Patients who discontinue study drug early will have investigations performed as indicated in footnote c (Early treatment discontinuation visit).
All other patients will continue to attend visits until Week 52 to obtain PK, PD, safety, efficacy, and immunogenicity data.
- c Patients who discontinue treatment at any time during the study after Day 1 (but do not withdraw their consent) will be required to have efficacy assessments at Week 28, or before a new anti-lymphoma treatment is started, and an early treatment discontinuation visit. If new treatment must be started before the Week 28 assessments, then the early treatment discontinuation visit, including a CT scan, should be performed before the start of the new treatment.
- d Unscheduled visits should be scheduled as per Investigator discretion. Table shows an example of assessments. Tests will be selected as per Investigator's discretion.
- e Inclusion and exclusion criteria to be re-checked on admission to the study site.
- f Body weight measurement required for BSA calculation; body weight is measured as part of the complete PE at other visits.

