3.2 Selection of Study Population

3.2.1 Inclusion Criteria

Patients may be entered in the study only if they meet all of the following criteria:

1. Male or female patients aged at least 18 years.
2. Histologically-confirmed, without B symptoms, Ann Arbor stage II to IVA NHL (CD20+ FL of Grades 1, 2, or 3a) (Appendix 5):
 - Patients can be entered based on a diagnosis of CD20+ follicular lymphoma confirmed at the investigational site. Archival tissue or slides must be sent to the central pathology reviewer for retrospective confirmation of diagnosis. Patients must have tissue or slide available for the central pathology review to be enrolled.
 - Patients having both diffuse and follicular architectural elements will be considered eligible if the histology is predominantly follicular (i.e., $\geq 50\%$ of the cross-sectional area), and there is no evidence of transformation to a large cell histology.
 - If the interval since tissue diagnosis of follicular lymphoma is >24 months prior to screening visit, diagnostic confirmation using either core needle or excisional lymph node biopsy (latter preferred) is required to confirm that the histology remains in one of the eligible categories.
 - Bone marrow biopsy alone is not acceptable.
3. Low tumor burden according to GELF criteria defined as:
 - a) Normal serum lactate dehydrogenase (LDH)
 - b) No mass ≥ 7 cm.
 - c) Less than 3 nodal sites, each with diameter >3 cm.
 - d) No systemic or B symptoms (fever $>38^{\circ}\text{C}$ for 3 consecutive days; recurrent, drenching night sweats; unintentional weight loss exceeding 10% body weight in the last 6 months.
 - e) No splenomegaly ≥ 16 cm by CT scan.
 - f) No risk of vital organ compression.
 - g) No pleural or peritoneal serous effusion.
 - h) No cytopenias (defined as platelets $<100 \times 10^9/\text{L}$ ($100,000/\text{mm}^3$), hemoglobin <100 g/L (10 g/dL), or absolute neutrophil count $<1.5 \times 10^9/\text{L}$ ($1,500/\text{mm}^3$)).

4. Patients not previously treated for their FL, including any previous treatment for FL under clinical trials except localized radiation therapy for previous limited stage disease.
5. Eastern Cooperative Oncology Group (ECOG) performance status of 0 to 1 (Appendix 6).
6. Have at least one measurable lesion of at least 1.5 cm in longest diameter as per the IWG criteria 2007 (Appendix 4) at screening (lesion clearly measurable in at least 2 perpendicular dimensions).

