4.0 STUDY TREATMENTS

4.1 Treatments Administered

Following randomization, SAIT101 or MabThera[®] treatment will be administered as an i.v. infusion once a week for 4 weeks, at a standard dose of 375 mg/m² body surface area. If the patient's weight changes by more than 10% before the next infusion, then BSA should be recalculated. Cycle 1 Day 1 study drug must be administered within 0 to 4 days after randomization.

Both treatments are anti-CD20+ antibody medications.

For study drug administration details, please see Section 4.5. For pre-medication administration details, please see Section 4.4 and Appendix 8.

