APPENDIX 10: SCHEDULE OF ASSESSMENTS

1. Screening (Visit 1 – Study Days -30 to 0)

The following screening procedures will be performed within 30 days prior to the first day of blinded study drug administration unless otherwise stated.

- Informed consent (must be obtained prior to the patient undergoing any study specific procedures and may occur prior to the 30 day screening period).
- Review inclusion /exclusion criteria.
- Record screening visit in the IXRS.
- Confirm diagnosis of Grade 1-3a, CD20+ FL and ensure tissue or slide is available for the retrospective central pathology review (Appendix 2). If a biopsy has not been performed within the previous 24 months prior to screening visit, a new biopsy is required to confirm that the histology is unchanged.
- Evaluate FL signs and symptoms and ensure the patient is not experiencing B symptoms.
- Ensure the patient is Ann Arbor Stage II, III, or IVA (Appendix 5).
- Collect information for FLPI-2 (Appendix 3).
- Collection of demographic information.
- Medical and surgical history.
- Adverse events.
- Prior and current medications.
- Physical examination (PE) The PE should include assessment of general appearance, skin, head, neck, throat, lymph nodes, thyroid, abdomen, cardiovascular, neurological, musculoskeletal/extremities, and respiratory systems, as appropriate, and consistent with local standard of care. Body weight will be measured. Height will be measured at screening only. The PE must include lymph nodes, liver and spleen. Any specific signs or symptoms that are medically significant should be reported. Particular attention should be paid to any new or worsening neurological symptoms or signs that may be suggestive of PML (typical symptoms are diverse and include cognitive or visual disorders, hemiparesis, confusion and behavioral disorders).
- Vital signs, including systolic and diastolic blood pressure, pulse, respiratory rate, and body temperature. To be measured after the patient has been in a sitting/lying down position for at least 5 minutes.

- ECOG performance status assessment
- 12-lead electrocardiogram (ECG).
- Laboratory testing including hematology, blood chemistry, urinalysis, serum β 2 microglobulin, lactate dehydrogenase (LDH), and viral disease screening (hepatitis B surface antigen, hepatitis B core antibody, and hepatitis C antibody, and HIV testing)

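### SAP Appendix 3 (Protocol Deviation Specification) does not match AGB 002: programmed as written, it can mark protocol-eligible patients as Major deviators for PP exclusion, and two of its rows cannot be evaluated

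*SAP*

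**What the plan says.** SAP 4.8 names a Protocol Deviation Specification as one source of the deviation criteria. It says the specification will be developed from a separate guidance and updated, and it does not cite Appendix 3 by number. Appendix 3 carries that title and shows seven rows, all graded Major: I01, E01, D01, C01, C02, C1E and C2E.

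- **Age (I01):** "Male or female age out of range (< 18 or >80 years) at Screening", PP exclusion *Yes*. Protocol 3.2.1 asks for "Male or female patients aged at least 18 years" and stops there.
- **Screening interval (C01):** "More than 6 weeks from Screening to randomisation (+1 week window allowed if the subject is still eligible at the Randomisation for ESR/CRP"; PP exclusion is *Yes*. Protocol Table 1, footnote a, says "Most screening assessments should be conducted within 30 days of Day 1" and lets the screening CT and marrow biopsy be earlier, adding "The total screening period is not to exceed 60 days in this case".
- **Prior treatment (E01):** "Previous usage of any biological agents including any TNF-alpha inhibitor prior to Randomisation", PP exclusion *Yes*, with a pointer to ATC codes for prohibited medication.

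The remaining rows concern continued dosing during serious infection (D01), a Week 24/Visit 5 window (C02), the timing of an ACR component, CRP (C1E), and chest X-ray timing (C2E). The table has exclusion columns for PP and PP2, and C2E refers to PPS1 and PPS2.

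SAP 4.8 and SAP 8 report programmed and site-reported Critical/Major deviations by treatment group for the RAN. SAP 4.5 sets the PPS conditions, and exclusions from it are decided at blinded review.

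**The concern.** A deviation specification turns eligibility and conduct rules into programmed flags. Here several flags are not this trial's rules. ACR components, ESR/CRP, TNF-alpha inhibitors and a Week 24/Visit 5 suggest a rheumatology study as the source. SAP 17.3 also lists erythrocyte sedimentation rate, C-reactive protein and rheumatoid factor, none of which is in protocol Table 2.

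Two outputs are at stake. The RAN table of Major deviations could count eligible patients as deviators and miss real ones. The blinded review could also start from wrong PPS flags, and the PPS feeds sensitivity analyses 1-2, 2-2 and 5-2.

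**Working it through.** No figure in the plan is in dispute. The check sets each row beside the protocol, with day counts for C01.

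| Row | PP exclusion | Protocol counterpart | Result if programmed as written |
|---|---|---|---|
| I01 | Yes | 3.2.1 criterion 1: lower limit of 18 only | Flags an eligible patient over 80 |
| C01 | Yes | Table 1 footnote a; Appendix 10 | Can err both ways (below) |
| E01 | Yes | 3.2.2 criterion 1: chemotherapy, rituximab or other monoclonal antibody | Wording is wider on biologics and silent on chemotherapy; actual reach depends on an ATC list not shown |
| C2E | Yes if over 100 days before Screening or after randomisation | Footnote t: X-ray only after a positive TB test; 3.2.2 criterion 12: counted from Day 1, chest CT also accepted | Can flag an X-ray the protocol never required; different starting point |
| C1E | Yes | No ACR assessment; no CRP in Table 2; drug is infused, not injected | Cannot be evaluated |
| C02 | No | No Week 24 visit; Visit 5 is Day 22 | Cannot be evaluated; could touch only the deviation table |
| D01 | No | 3.3.1.2 | Not disputed |

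Neither document defines PP2, PPS1, PPS2 or Study Part A, B. SAP 4.5 has one PPS plus a PET-CT subset.

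**C01 inputs.** Let *s* be the days from a screening assessment to randomisation and *g* the days from randomisation to Day 1. Protocol 4.1 gives *g* = 0 to 4: "Cycle 1 Day 1 study drug must be administered within 0 to 4 days after randomization". C01 flags *s* > 6 × 7 = 42, or *s* > 49 if the extra week is granted. That extra week depends on ESR/CRP, which protocol Table 2 does not list.

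**Flagged although allowed (early CT or biopsy).** Footnote a counts the 60 days for CT and biopsy to randomisation, so *s* ≤ 60. Appendix 10 counts the CT's 60 days to Day 1, so *s* ≤ 60 − *g*, which is 56 when *g* = 4.
- Limit at 60: days 43–60, 60 − 42 = 18 days; with the extra week, days 50–60, 60 − 49 = 11 days.
- Limit at 56: days 43–56, 56 − 42 = 14 days; with the extra week, days 50–56, 56 − 49 = 7 days.

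**Passed although late (assessments under the 30-day limit).** Appendix 10 also counts this limit to first dosing: "The following screening procedures will be performed within 30 days prior to the first day of blinded study drug administration unless otherwise stated". So *s* ≤ 30 − *g*.
- *g* = 0: days 31–42, 42 − 30 = 12 days; with the extra week, 49 − 30 = 19 days.
- *g* = 4: days 27–42, 42 − 26 = 16 days; with the extra week, 49 − 26 = 23 days.

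These counts apply to assessments. Footnote a says most assessments *should* meet the limit, Appendix 10 lets consent come earlier, and C01 does not say what Screening refers to. Early consent alone is therefore not a deviation.

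**The case against.** The strongest reply is that the plan does not say these rows will be programmed as they stand. SAP 4.8 describes a specification still to be developed and updated, and the guidance behind it is a separate document not seen here. The SAP body cites Appendices 1 and 2 by number but never Appendix 3. The few rows, the broken code sequence and the empty PK/PD columns look like an extract. SAP 4.5 states the PPS conditions, blinded review decides exclusions before unblinding, and the FAS is primary.

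Most of this stands and limits the consequence. It does not remove the defect: the SAP is marked Final v1.0, the appendix bears the title SAP 4.8 uses, and nothing shown marks it as a sample. A header containing the word *Simple* is ambiguous. If the table is a placeholder, the SAP contains no AGB 002 specification, and the remedy is the same. Nor does the text say that blinded review of the analysis sets corrects the RAN deviation table.

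Three stronger readings should be resisted:
- *The PPS will omit its own grounds.* No specific row covers central pathology, wrong drug, fewer than four infusions or prohibited on-study treatment, and E01 does not mention chemotherapy. SAP 4.5 states those grounds and covers unmet eligibility criteria, so they are missing from the table, not from the plan.
- *C2E tolerates X-rays too old for eligibility.* Its 100-day figure triggers PP exclusion only; the row already grades X-rays over 3 months before Screening as Major. Exclusion 12 also accepts chest CT, which protocol 5.1.1 schedules at baseline, so an old X-ray need not breach it. Footnote t still asks for an X-ray after a positive TB test.
- *C01's error is a fixed number of days.* It depends on the anchor, as shown above.

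**Conclusion.** The mismatch is certain; its effect is conditional on the table being programmed as written. In that case I01, C01, E01 and C2E could flag patients who meet the protocol (E01 subject to the unseen ATC list), C01 could also pass assessments done more than 30 days before Day 1, and C02 and C1E could not be evaluated.

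The day counts for C01 are 7 to 18 days flagged although allowable, and 12 to 23 days passed although late, depending on the extra week, the anchor and the gap to dosing. The number of patients affected and the net direction are unknown. A reader might infer lost power or bias in the PPS analyses, but the documents give no exclusion counts from which to estimate either.

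The FAS primary analysis is unaffected. This should be fixed, at the low end of that grade.

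**What to change.** Before the blinded data review and unblinding:

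- Replace Appendix 3 with a table built from AGB 002's own criteria, and cite it by number in SAP 4.8.
- Map each criterion in protocol 3.2.1 and 3.2.2 and each SAP 4.5 condition to a single PPS flag.
- In I01, keep the lower age limit and remove the limit of 80.
- Restate C01 with the protocol's 30- and 60-day limits, define the starting event, and say whether each limit counts to randomisation or Day 1. Table 1 footnote a and Appendix 10 differ on this and must be reconciled.
- Align E01 with exclusion 1, and C2E with exclusion 12 and footnote t.
- Delete C02 and C1E, and the PP2, PPS1/PPS2 and Study Part labels.
- Reconcile the ESR, CRP and rheumatoid factor entries in SAP 17.3 with protocol Table 2.

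The cost is one rewritten appendix, one cross-reference and one sentence in SAP 17.3, plus settling the anchor between the two protocol passages. It needs no new data and no change to the sample size or primary analysis.
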